## 6.6 Early Termination Visit

The clinic will make every effort to perform all assessments outlined for the Final Study Visit (Day 21±2) if a subject is terminated prematurely from the study. All information collected will be documented in the study records including eCRF.

## 6.7 Unscheduled Study Visits

Subjects will return to the CRU at the direction of the site investigator for follow-up and data from unscheduled visits or procedures (if any) will be captured in the EDC system. Safety assessments including the following onsite evaluations: AE, PE, and any other study procedures deemed necessary by the PI will be obtained.

Subjects returning to the CRU for Unscheduled visit(s) may undergo procedures as indicated in the Schedule of Study Procedures and Evaluations ([Appendix A](#) VT-1598 Schedule of Study Procedures and Evaluations) and as detailed in [Section 7](#) Description of Clinical and Laboratory Evaluations Study, Procedures/Evaluations: listed below:

- Review and record any concomitant medications and non-pharmacologic treatments/procedures since last visit;
- standard 12-lead ECG (recording in triplicates) to assess heart rate, rhythm, and interval information such as PR, QRS, QT, QTc and QTcF, obtained after at least 5 minutes in the supine position;
- obtain blood samples for clinical chemistry, hematology, and coagulation tests;
- obtain blood sample for PK analysis;
- obtain urine sample for urinalysis.
- targeted physical examination (general appearance, heart, lungs, skin and abdomen; additional evaluation will be targeted to the suspected organ system described in any AE.) including resting vital signs (heart rate, blood pressure, oral temperature and respiration rate, taken after being at rest for at least 5 minutes. If abnormal, these measurements may be repeated once, within 15 minutes of the original assessment;
- collect and record adverse events (AEs).

## 6.8 Protocol Deviations

A protocol deviation is any noncompliance with the clinical trial protocol, GCP, or protocol-specific MOP requirements. The noncompliance may be either on the part of the subject, the site principal investigator, or the site personnel. As a result of deviations, corrective actions are to be developed by the site and implemented promptly.

These practices are consistent with ICH E6:

4.5 Compliance with Protocol, Sections 4.5.1, 4.5.2, and 4.5.3

5.1 Quality Assurance and Quality Control, Section 5.1.1

5.20 Noncompliance, Sections 5.20.1, and 5.20.2.

It is the responsibility of the site principal investigator and personnel to use continuous vigilance to identify and report deviations within five working days of identification of the protocol deviation, or within five working days of the scheduled protocol-required activity. All deviations must be promptly reported to DMID per the SDCC protocol deviation reporting procedures.

All protocol deviations, as defined above, must be addressed in study subject data collection forms. A completed copy of the DMID Protocol Deviation Form must be maintained in the Regulatory File, as well as in the subject's chart. Protocol deviations must be sent to the local IRB per their guidelines. The site principal investigator and personnel are responsible for knowing and adhering to their IRB requirements.

## 7 DESCRIPTION OF CLINICAL AND LABORATORY EVALUATIONS

### 7.1 Clinical Evaluations

#### 7.1.1 Safety Tests and Assessments

Safety assessments will include attention to relevant changes in the following parameters, which are identified as occurring after the start of study product, regardless of whether the change is in an examination finding, test result, or symptom(s) reported by a subject, and regardless of presumed relationship to VT-1598.

##### **Height, Weight, BMI**

Height and/or body weight will be collected at times specified in the Schedule of Assessments and Procedures [Appendix A](#) VT-1598 Schedule of Study Procedures and Evaluations. BMI is calculated from height at Screening and weight at time of assessment.

##### **Vital Signs**

Vital signs (resting) to include body temperature, heart rate (pulse), breathing rate, and blood pressure will be obtained at times specified in the Schedule of Assessments and Procedures [Appendix A](#) VT-1598 Schedule of Study Procedures and Evaluations. Vital signs should be taken after at least 5 minutes at rest. If abnormal, these measurements may be repeated once, within 15 minutes of the original assessment.

The pre-dose Day 1 vital signs measurements should be taken any time within 60 minutes prior to dosing (within 30 minutes prior to the start of the pre-dose meal for the fed cohort). Day 1 post-dose vital signs measurements should be taken within  $\pm 10$  minutes of the nominal timepoint. All other vital signs measurements during the inpatient stay should be taken within  $\pm 30$  minutes of the nominal time point. For outpatient visits, vital signs measurements should be taken within the visit window.

##### **Physical Exam**

A complete physical examination will include review of resting vital signs (taken after being at rest for at least 5 minutes); general appearance; head, eyes, ears, nose, and throat; neck; chest and lungs; cardiovascular system, abdomen, musculoskeletal system, lymph nodes, extremities/skin, and neurological system will be performed at Screening.

A targeted physical examination (general appearance, heart, lungs, skin and abdomen) will include review of the resting vital signs which will be taken at 72 hours ( $\pm 30$  min) post-dose and

---

after being at rest for at least 5 minutes. Additional evaluation will be targeted to the suspected organ system described in any AE. Targeted physical examinations will be performed at times specified in the Schedule Assessments and Procedures [Appendix A](#) VT-1598 Schedule of Study Procedures and Evaluations .

### **Electrocardiograms**

Standard 12-lead ECGs to assess heart rate, rhythm, and interval information such as PR, QRS, QT, and QTc will be obtained at times specified in the Schedule of Assessments and Procedures [Appendix A](#) VT-1598 Schedule of Study Procedures and Evaluations. The QT interval will be corrected using the Fridericia formula (QTcF).

Electrocardiograms should be taken after at least 5 minutes in the supine position. The pre-dose Day 1 ECGs should be taken within 60 minutes prior to dosing (within 60 minutes prior to dosing for the fed cohort); the post-dose ECG on Day 1 should be taken at 4 hours post-dose ( $\pm$  30 minutes). The Day 4 ECG should be taken at 72 hours ( $\pm$  30 minutes) post-dose. For the Day 21 outpatient visit, the ECG should be taken within the visit window.

Subjects will be placed in a supine position for at least 5 minutes prior to recording an ECG. Triplicate 12- lead ECG readings will be collected at scheduled times as shown in [Appendix A](#) VT-1598 Schedule of Study Procedures and Evaluations . The screening ECG will be used by the PI to determine subject's eligibility for enrollment. The Day 1 pre-dose ECG will be reviewed to determine if subjects are safe and appropriate to dose and will be used to determine baseline for waveform and QTc.

All ECGs will be reviewed by the PI or designee. ECGs with the following readings will be considered acceptable for study and will not be considered abnormal for study purposes unless the PI or physician designee believes they represent a new medical condition when compared to baseline ECGs. In such cases an AE will be documented, and the subject will be followed for safety evaluations as appropriate. The following pre-existing conditions identified at enrollment will not be considered adverse events and will be documented on the Medical History eCRF:

- Sinus bradycardia;
- Sinus arrhythmia.

Subjects without a history of prolonged QTc and an abnormal baseline QTcF interval (not meeting exclusion criteria) should undergo repeat ECG assessment within screening period prior to randomization to confirm prolongation. If the repeat ECG QTcF is within normal limits the subject may be considered for enrollment

---

The Sponsor may review all or individual screening or Day 1 ECGs or may delegate to PI determine if meets intention of entry criteria goal of enrolling healthy normal study subjects.

The mean of triplicate QTcF measurements post-dose will be used to assess QTcF prolongation (including assessment of halting rules described in [Section 8.6](#)), and will be compared to the mean of the baseline measurements to calculate change from baseline.

In the event of a prolongation of QTc post dosing, the site will start telemetry monitoring of the subject and capture triplicate 12 lead ECG (3 tracings within a 5-minute period) every 30 minutes ( $\pm 10$  minutes) until the average for the triplicates has returned within 60ms of the baseline value at which time telemetry may be discontinued. Persistent (1 hour or more) elevation in QTcF ( $>500$ ms) should prompt immediate consideration of transfer to appropriate emergency department for further evaluation, monitoring, and/or treatment.

In the event of a change in ECG wave forms consistent with a change in cardiac function or conduction when compared to baseline tracings, or in the event of a subject with possible cardiac related symptoms, repeat ECG should be obtained every 30 minutes ( $\pm 10$  minutes) until wave form change reverts to baseline appearance, or symptoms resolve, or are determined not to be cardiac in origin. Subjects with cardiac related symptoms associated with ECG changes will be transferred to appropriate emergency department for further evaluation and treatment.

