### 5.1.2 Subject Exclusion Criteria

1. has a chronic condition that may increase risk to subject or interfere with endpoint assessment (e.g., liver disease, kidney disease, immunodeficiency).
2. Chronic condition diagnosed within 90 days of the screening visit
3. Unstable chronic disease\* within 6 months of the screening visit  
     \*as defined by need for medical intervention that lead to a change in medications and/or required hospitalization, surgery/procedure, or ED/urgent care visit
4. History of psychiatric condition that has required hospitalization in the last 5 years or patient is considered unstable by study investigator
5. Any condition that in the opinion of the Investigator could significantly impact drug absorption, distribution, or elimination;
6. Any out of normal range laboratory value\* at screening or enrollment ([Section 8.1](#) and [Appendix B](#)).

\*A laboratory value that is Grade 1 (with the exception of ALT, AST, Total bilirubin, hemoglobin or serum creatinine) will be allowed if not considered to be clinically significant by the investigator.

7. Abnormal ECGs. See [Section 7.1](#) Clinical Evaluations for exceptions;
8. Electrocardiographic QTcF interval  $>430$  msec for males and  $>450$  msec for females at Screening;
9. Positive test for antibodies to HIV-1, HIV-2, HBsAg, or HCV;
10. Positive urine drug test. The drugs that will be screened for includes amphetamines, barbiturates, cocaine, opiates, cannabinoids, phencyclidine, and benzodiazepines.

- 
11. Female subject of childbearing potential who is pregnant\*, lactating, or planning to become pregnant during the study period or 3 months after the final dose of study product;  
\*Having a positive serum pregnancy test at the Screening Visit or any other specified time point prior to the dose of study product.
  12. Received any study product in a clinical trial within 30 days prior to Screening;
  13. Admitted or documented illicit drug use or alcohol abuse within 6 months prior to Screening or during their participation in the trial;
  14. Consumed alcohol within 72 hours of Day -1, until after the visit to the CRU on Day 14 or have a positive alcohol test at Screening or on admission to the CRU;
  15. Tobacco\* use within 90 days prior to the Screening Visit or while a subject is enrolled in the study OR A positive urine drug test for cotinine;  

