
Adverse Events*	Mild (Grade 1)	Moderate (Grade 2)	Severe (Grade 3)
-----------------	-------------------	-----------------------	---------------------

\*\* Hematuria during active menses is considered not clinically significant.

Vital Sign Adverse Events	Mild (Grade 1)	Moderate (Grade 2)	Severe (Grade 3)
Fever (°C)	38.0 – 38.4	38.5 – 38.9	39.0 – 40
(°F)	100.4 – 101.1	101.2 – 102.0	102.1 – 104
ECG – QTcF (ms)	> 30 but ≤60 above baseline	>60 above baseline to ≤500	>500
Tachycardia – (beats per minute)	101 – 115	116 – 130	>130
Bradycardia – (beats per minute)	50-54 if baseline >60	45-49 if baseline >60	<45 if baseline >60
	45-50 if baseline ≤ 60	40-44 if baseline ≤ 60	<40 if baseline ≤ 60
Hypertension (systolic) – mmHg	141 – 150	151 – 155	>155
Hypertension (diastolic) – mmHg	91 – 95	96 – 100	>100
Hypotension (systolic) – mmHg	85 – 89	80 – 84	<80
Respiratory Rate – breaths per minute	17-20	21-25	>25
Nausea/vomiting	No to mild interference with activity or 1 to 2 episodes/24 hours	Moderate interference with activity or >2 episodes/24 hours	Prevents daily activity, requires outpatient IV hydration
Diarrhea	2 - 4 loose stools or	5-6 stools or 400 – 800	7 or more watery stools or >800gms/24 hours or

Vital Sign Adverse Events	Mild (Grade 1)	Moderate (Grade 2)	Severe (Grade 3)
	< 400 gm/24 hours	gm/24 hours	requires outpatient IV hydration
Headache	No interference with activity	Repeated use of non-narcotic pain reliever > 24 hours or some interference with activity	Significant; any use of narcotic pain reliever or prevents daily activity
Fatigue	No interference with activity	Some interference with activity	Significant; prevents daily activity
Adverse Events – Other			
Illness or clinical AE (as defined according to applicable regulations)	No interference with activity	Some interference with activity, not requiring medical intervention	Prevents daily activity and requires medical intervention

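### The rule for stopping post-dose telemetry has no absolute QTcF ceiling, so for a Day 1 baseline above 440 ms it permits stopping while mean QTcF is still above 500 ms (Grade 3)

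*Protocol*

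**What the plan says.** Protocol 7.1.1, Electrocardiograms, compares the mean of the post-dose triplicates with the mean of the baseline measurements. If QTc is prolonged after dosing, the site starts telemetry and repeats the triplicates at half-hourly intervals, with a window of 10 minutes either way, "until the average for the triplicates has returned within 60ms of the baseline value at which time telemetry may be discontinued". SAP 4.5 restates the 60 ms condition, also without an absolute limit.

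The surrounding provisions are these:

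- **Baseline.** The Day 1 pre-dose ECG "will be used to determine baseline for waveform and QTc". It is reviewed for fitness to dose, but no numeric QTcF cap applies to it.
- **Entry limits.** Exclusion 8 (Protocol 5.1.2, repeated in SAP 4.3) bars QTcF above 430 ms in men and above 450 ms in women, at Screening.
- **Grading.** Appendix B defines Grade 2 as ">60 above baseline to ≤500" and Grade 3 as anything above 500 ms, whatever the change.
- **Transfer.** The sentence after the stop rule says that "Persistent (1 hour or more) elevation in QTcF" above 500 ms should prompt immediate consideration of transfer to an emergency department.
- **Halting.** The cohort rule in 8.6.2 counts a subject with QTcF above 500 ms or a change above 60 ms, as alternatives.

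**The concern.** Grading, halting and the transfer sentence each treat QTcF above 500 ms as important in its own right. The stop rule uses change from baseline alone. In a subject whose baseline is already fairly long, a reading can be back within 60 ms and still be above 500 ms.

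What is at stake is the 1-hour check. If monitoring ends at the first 30-minute repeat, nobody has the readings to tell whether the elevation lasted an hour. The only scheduled post-dose ECG on Day 1 is at 4 hours, so stopping at the first repeat would fall at about 4.5 hours. That is before the 6-hour time at which Section 9.3 presumes Cmax. The next scheduled ECG is at 72 hours (6.3.3). This is a first-in-human study.

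**Working it through.** The plan states no figure to reproduce; the check is direct arithmetic on its thresholds.

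**Inputs.** Stop condition: change of at most 60 ms (7.1.1, SAP 4.5). Grade 3: above 500 ms (Appendix B). Screening caps: 430 ms for men, 450 ms for women (5.1.2). Persistence criterion: 60 minutes (7.1.1). Repeat interval: 30 ± 10 minutes (7.1.1).

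**Break-even baseline.** Highest stopping value = baseline + 60. This exceeds 500 when baseline > 500 − 60 = 440 ms. The values are means of triplicates, so the boundary is anything above 440 ms, not 441 ms.

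| Day 1 baseline (ms) | Highest stopping value (ms) | Width of the range above 500 ms in which stopping is allowed | Change from baseline in that range |
|---|---|---|---|
| 430 | 490 | none | none |
| 440 | 500 | none | none |
| 445 | 505 | 505 − 500 = 5 ms | above 55, up to 60 ms |
| 448 | 508 | 508 − 500 = 8 ms | above 52, up to 60 ms |
| 450 | 510 | 510 − 500 = 10 ms | above 50, up to 60 ms |

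The 510 ms figure belongs to a 450 ms baseline and is not a maximum. The Day 1 baseline has no numeric cap, and a drift to 460 ms would give 520 ms.

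**Who is affected.** At the Screening limits, women with baselines above 440 and up to 450 ms. A man at his cap stops at 430 + 60 = 490 ms; he is affected only if his Day 1 baseline exceeds 440 ms, a rise of more than 440 − 430 = 10 ms since Screening.

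**Illustration (invented readings).** Baseline 448 ms.

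1. The 4-hour triplicate mean is 515 ms. Change: 515 − 448 = 67 ms, above 60, so monitoring starts.
2. The next triplicate, 30 minutes later, is 505 ms. Change: 505 − 448 = 57 ms, so the stop condition is met.
3. The change of 57 ms lies in the Grade 1 band (above 30, up to 60 ms), but 505 ms is above 500 and therefore Grade 3.
4. Time documented above 500 ms is 30 minutes (20 to 40 with the window), against the 60 needed for the transfer criterion.

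**With a ceiling added.** Highest stopping value = min(baseline + 60, 500). At a 450 ms baseline it falls from 510 to 500 ms; at 440 ms or below nothing changes. In the illustration, 505 ms no longer qualifies and the 60-minute triplicate is taken. If that is, say, 498 ms (498 − 448 = 50 ms), monitoring may stop after one extra triplicate.

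**The case against.** The strongest reply is that the paragraph should be read whole. The 1-hour sentence cannot be applied without a reading at about 60 minutes, so it implies one, and the stop clause says only that telemetry may be discontinued. That stands as far as it goes. But the sentence prompts consideration of transfer; it does not alter the stop condition, and the stop clause does not require the 60-minute reading.

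There are also real safeguards. The investigator or a designee reviews all ECGs. A subject with an abnormal baseline QTcF short of exclusion "should undergo repeat ECG assessment within screening period prior to randomization to confirm prolongation". Wave-form change triggers repeat ECGs, and "in the event of a subject with possible cardiac related symptoms, repeat ECG should be obtained every 30 minutes"; the gap therefore concerns a subject with neither. Unscheduled ECGs are available (6.7), adverse events are followed to resolution or stabilization (8.1.1, 8.4), and subjects stay at least 72 hours (3.1.2). For sentinels only, a Grade 2 or higher event not resolved within 1 day through Day 3 suspends the cohort (8.6.2), which in practice calls for a repeat ECG. These narrow the gap, but none gives a QTcF value for stopping.

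The nonclinical data are fairly reassuring: no QTc change in telemetered monkeys, and a mild increase only at the top dose of the 28-day monkey study (2.1).

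A reader might also infer that the trigger for starting telemetry is undefined. The documents do not support that. The preceding sentence says the mean of the post-dose triplicates "will be used to assess QTcF prolongation (including assessment of halting rules described in" Section 8.6, and a return to within 60 ms presupposes an excursion beyond it.

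**Conclusion.** The point holds and is minor: a cheap improvement to subject monitoring. For any Day 1 baseline mean above 440 ms, the stated rule permits telemetry and 30-minute triplicates to stop at a value the protocol grades as severe, up to 510 ms at a 450 ms baseline. This takes the stop clause at its word and counts a change of exactly 60 ms as within 60 ms; if 60 were excluded, the 440 ms boundary would not move.

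Two stronger readings should be resisted. One is that the protocol directs sites to stop monitoring at Grade 3 values; it only permits this, and the neighbouring sentence points the other way. The other is that the trial's safety conclusions are affected. A reading above 500 ms counts toward the halting rule and is graded whether or not telemetry continues, so no endpoint, halting count or analysis changes.

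How many subjects could be affected cannot be said. The documents give no distribution of baseline QTcF, no rate of prolongation, and no numeric normal limit for the repeat-ECG rule.

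**What to change.** In Protocol 7.1.1, insert *and is ≤500 ms* immediately after the reference to the baseline value, so that stopping requires both a mean within 60 ms of baseline and a mean no higher than 500 ms. Make the same insertion in SAP 4.5 for consistency; it changes no analysis. The threshold is the protocol's own.

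As an optional clarification, state the starting trigger in the same sentence as mean QTcF above 500 ms or more than 60 ms above baseline, the 8.6.2 thresholds to which the paragraph already points.

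The cost is one phrase in each document. The downside is a few extra 30-minute triplicates, continuing while the mean stays above 500 ms, in a rare subject who is already an inpatient.

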### **7.1.2 Assessment of Concomitant Medications/Treatments other than Study Product Prohibited Medications/Non-Medications**

Subjects are required to abide by the following rules regarding intake of medications and other substances before and during the study:

- Refrain from the use of all prescription medications (with the exception of hormonal contraceptives), including any type of prescription antibiotic drug (topical or systemic) for at least 14 days prior to administration of the dose of study product on Day 1 until after the final study visit to the CRU;
- refrain from the use of all non-prescription medications, vitamins, or dietary supplements, within 7 days prior to administration of the dose of study product on Day 1 until after the visit to the CRU on Day 14;
- herbal supplements must be discontinued 7 days prior to the dose of study product on Day 1 until after the visit to the CRU on Day 14;

- 
- the consumption of beverages and foods containing alcohol is prohibited for 72 hours prior to Day -1 until after the visit to the CRU on Day 14. A urine alcohol test will be performed at Screening and upon admission to the CRU;
  - the consumption of beverages and foods containing caffeine is prohibited for 24 hours prior to Day -1 until discharge from the CRU on Day 4;
  - consumption of grapefruit, grapefruit juice, or juices containing grapefruit, or Seville oranges is prohibited within 7 days prior to the dose of study product until after the visit to the CRU on Day 14;
  - the use of tobacco product, including smoking and the use of snuff and chewing tobacco, and other nicotine or nicotine-containing products, is not permitted by a subject within 90 days of Screening for the study or while a subject is enrolled in the study. A urine test for cotinine will be performed at Screening and upon admission to the CRU;
  - the use of illegal drugs is not permitted while a subject is enrolled in this study. A urine drug test, including amphetamines, barbiturates, cocaine, opiates, phencyclidine, cannabinoids and benzodiazepines, will be performed at Screening and upon admission to the CRU.

If a subject is unable to comply with the restrictions described above, the subject's continued participation in the study will be re-evaluated by the Investigator, in consultation with the Medical Monitor.

